2.2 OBJECTIVES

2.2.1 Primary Objective

The primary objective is to evaluate the safety and efficacy of 3 different doses of oral plecanatide taken once daily for 8 weeks as treatment for CIC in adolescents 12 to less than 18 years of age.

2.2.2 Secondary Objectives

Secondary objectives are:

- To estimate the pharmacokinetic (PK) parameters of plecanatide in this patient population (to the extent possible, since plecanatide is not expected to be absorbed)
- To evaluate the effect of 3 selected dose levels of plecanatide on stool consistency and relief of CIC-related symptoms in adolescents 12 to less than 18 years of age
- To assess the effect of 3 selected dose levels of plecanatide on the frequency of complete spontaneous bowel movements (CSBMs)

2.2.3 Rationale for Dose Selection

Safety and efficacy data with plecanatide in adult CIC clinical trials performed to date has defined a safe and effective dose roughly in the range of 0.05 mg/kg to 0.1 mg/kg. Data suggest that children aged 4 years through 16 years appear to have a GC-C receptor density more reflective of a “mature” intestine (Cohen, 1988). Although safety of a particular dose cannot be taken for granted, it is more likely that children in this age group will respond to a GC-C agonist similarly to adult patients. Thus, the expectation is that ≤ 0.05 mg/kg should represent safe and effective doses for treatment of CIC in adolescents ages 12 to 17 years under study in this protocol. There are few data that might shed light on potential physiological differences between adults and children in terms of pharmacological dose-responsiveness to GC-C agonists.

Based on considerable PK experience in the adult population it is known that plecanatide is essentially unabsorbed from the human GI tract in the dose range proven effective for the treatment of adult CIC. There is no expectation that pediatric patients will differ in this respect. Therefore, the doses selected for an adolescent population are anticipated to be safe and well tolerated.

2.3 RISK-BENEFIT ASSESSMENT

The most common TEAEs in adult patients treated with plecanatide have been diarrhea and other gastrointestinal (GI)-related symptoms such as abdominal cramps, gas, and bloating Investigator Brochure (IB) Ed. 8.0 for Plecanatide, 1/2016. It is expected that the plecanatide safety profile observed in the 12 to < 18-year old pediatric population will be similar to that observed in adult patients with CIC.

The amount of blood to be drawn during the course of this study (approximately 57 mL for the majority of patients, and 81 mL for patients participating in the intensive PK analysis) is not considered to be a risk to adolescent patients qualified for enrollment in this study.

2.4 CRITERIA FOR EVALUATION OF THE STUDY

The efficacy and safety endpoints are described below. For information concerning the analyses of these endpoints, see **Section 8.8** and **Section 8.10** respectively.

2.4.1 Efficacy Endpoints

2.4.1.1 Primary Efficacy Endpoint

The primary efficacy endpoint is the proportion of responders for the last 2 weeks of the Treatment Period (responder = a child who experiences >3 SBMs per week for each of the last two weeks of the treatment period) compared to placebo and across treatment groups.

2.4.1.2 Secondary Efficacy Endpoints

The secondary efficacy endpoints are:

- Change from baseline in weekly average stool consistency (BSFS) score over the 8-week treatment period, and by study week
- Change from baseline in the weekly rate of SBMs, by study week
- Change from baseline in the weekly rate of CSBMs over the 8-week treatment period, and by study week

2.4.1.3 Additional Efficacy Endpoints

Additional efficacy endpoints related to CIC symptoms are:

- Change from baseline in abdominal pain, by study week
- Change from baseline in abdominal bloating, by study week
- Change from baseline in straining during a BM, by study week
- Change from baseline in pain with defecation, by study week
- Change from baseline in excessive flatulence, by study period
- Change from baseline in frequency of fecal incontinence, by study period

2.4.1.4 Patient Reported Outcomes

The following patient reported outcomes will be assessed (see **Appendix E** for the assessment instruments used for these endpoints):

- PGA
- PAC-SYM
- PAC-QOL

2.4.1.5 Exploratory Efficacy Endpoints

The following exploratory endpoints will be assessed (see **Section 8.8.4** for definitions of these endpoints):

- 4/8 Week SBM 3 + 1 Responder
- 6/8 Week SBM 3 + 1 Responder
- 4/8 Week CSBM 3 + 1 Responder
- 6/8 Week CSBM 3 + 1 Responder

2.4.2 Pharmacokinetic Endpoints

Single dose and steady state PK of plecanatide and its major metabolite SP-338 (population modeling):

- Plasma concentration of plecanatide and SP-338 (Note: measurable plecanatide/SP-338 levels have not been observed in the adult population)
- PK parameters, including C_{max} , T_{max} , and C_{min} (only if sufficient number of plecanatide levels can be measured to allow computation of these parameters)

2.4.3 Safety Endpoints

The following safety endpoints will be assessed:

- Frequency of treatment-emergent adverse events (TEAEs)
- Withdrawals due to adverse events and serious adverse events

Clinically important changes in laboratory tests, vital signs, and ECGs will be presented.

2.5 JUSTIFICATION OF THE STUDY DESIGN

This is a randomized, double-blind, placebo-controlled, parallel group, Phase 2b study evaluating plecanatide 8-week treatment in adolescent patients with CIC.

Randomization and double-blind components of the study design are used to minimize bias in treatment group assignment and investigator/study personnel/patient bias, respectively, during the study. The fixed dose and time on study drug are the most objective ways to assess the therapeutic effect and safety of an investigational agent relative to placebo. The treatment period is 8 weeks, which is sufficient time to test the durability of response.

2.6 PLANNED SAMPLE SIZE AND NUMBER OF STUDY CENTERS

Approximately 120 patients (~ 30 patients per treatment group) will be recruited for this study at approximately 40 clinical sites in the USA. The patients will be enrolled in this multi-center outpatient study by gastroenterologists, internists, and general medicine practitioners who have been qualified as Investigators.

3 STUDY POPULATION

Patients must meet all of the inclusion criteria and none of the exclusion criteria listed below to be enrolled in the study.

3.1 INCLUSION CRITERIA

A patient will be eligible for study participation if he or she meets all of the following criteria:

1. Male or female adolescents 12 to less than 18 years of age.
2. Diagnosed with CIC based on the Rome III criteria for child/adolescent functional constipation (**Appendix A**).
3. Patient is able to voluntarily provide written, signed, and dated (personally and via a legally authorized representative [LAR]) assent/informed consent as applicable to participate in the study.
4. Patient and patient's parent/LAR demonstrates an understanding, ability, and willingness to fully comply with study procedures (e.g., acceptance of venipuncture, patient willing and able to swallow tablets, acceptance of urine drug screen for opiates) and restrictions.

3.2 EXCLUSION CRITERIA

A patient will be excluded from the study if he or she meets any of the following criteria:

1. The patient has a mental age <4 years in the investigator's opinion.
2. The patient has previously been diagnosed with anorectal malformations, neurological deficits, or anatomical anomalies that would constitute a predisposition to constipation.
3. The patient currently requires iron supplements, amitriptyline, or other tricyclic antidepressants for depression, opioid-containing medications or compounds for pain, or has other conditions that require medications known to cause constipation. A patient with an onset of constipation prior to the use of these medications and who has been on a stable dose for at least 8 weeks prior to Screening might be considered eligible for this study if the investigator deems these medications do not significantly contribute to the patient's constipation. Screening of these patients needs to be approved by the medical monitor and the sponsor.
4. The patient is pregnant or lactating.
5. The patient, if female of childbearing potential (defined as postmenarche), does not agree to practice 1 of the following medically acceptable methods of birth control throughout the study:
 - Hormonal methods such as oral, implantable, injectable, vaginal ring, or transdermal contraceptives for a minimum of 1 full cycle (based on the patient's usual menstrual cycle period) before study drug administration.
 - Total abstinence from sexual intercourse since the last menses before study drug administration.
 - Intrauterine device.

- Double-barrier method (condoms, sponge, or diaphragm with spermicidal jellies or cream).

6. The patient follows a diet not considered normal by the investigator for the patient's age, relative to variety of food, caloric content, and quantity. The patient must have been on a stable diet for at least 30 days weeks prior to Screening.
7. The patient's mobility or normal exercise tolerance is compromised in the investigator's opinion.
8. The patient has a history of an eating disorder.
9. The patient has clinical or laboratory signs and symptoms of significant cerebral, respiratory, renal, hepatobiliary, pancreatic, intestinal (including acute appendicitis, inflammatory bowel disease, or undiagnosed abdominal pain), endocrinologic, or infectious disease that in the investigator's judgment could interfere with study assessments or completion of the study. (Note: A patient with a history of thyroid disease may be enrolled if he or she has normal T3 and T4 at Screening. If the patient is taking medication for active thyroid disease, his or her T3 and T4 level must be within normal limits and the dose of any medication used to treat it must be stable for at least 30 days prior to Screening.)
10. The patient has any other medical condition or is receiving concomitant medication or therapy that would in the investigator's opinion compromise his or her safety or compliance with the study protocol or compromise data collection.
11. The patient has a history or evidence of drug or alcohol abuse in the 12 months before Screening.
12. The patient has a hypersensitivity, allergy, or contraindication to plecanatide.
13. The patient has received any experimental drug, including linaclotide and lubiprostone, or experimental therapy within 30 days of study start.
14. The patient is unable to tolerate protocol-prescribed rescue medication (Dulcolax®), or unwilling to use it as the only laxative for the duration of the trial.
15. The patient has taken a protocol-prohibited medication prior to randomization.
16. The patient and his or her parent/guardian are unable to communicate well with the study staff and comply with the study requirements (restrictions, appointments, and examination schedule). (The patient must be able to complete all required Daily BM and Symptom electronic diary entries during the Screening/Baseline period and for the duration of the study. The patient must also agree to receive a reminder daily via phone should he or she not complete the daily electronic diary entries.)

Exclusion Criteria Based on Baseline Diary Entries

17. Completion of < 5 of the 7 required daily diary entries in each week of the 2-week baseline diary assessment.
18. Use of rescue medication (Dulcolax®, bisacodyl) for more than 2 days during either of the two weeks of the 2-week baseline diary assessment.
19. ≥ 3 SBM per week for either week of the 2-week baseline diary assessment.

3.3 PREVIOUS AND CONCOMITANT MEDICATIONS

Any medication the patient takes other than the study drug, including herbal and other non-traditional remedies, is considered a concomitant medication. The following information must

be recorded in the eCRF for each concomitant medication: generic name, route of administration, start date, stop date, dosage, and indication. Any changes in the dose or regimen of a concomitant medication must also be recorded in the eCRF.

At the Screening visit, patients will be asked what medications they have taken during the last 30 days. At each subsequent study visit, patients will be asked what concomitant medications they are currently taking. Use of rescue medication will be recorded daily in the BM Diary and should not be included under concomitant medications.

3.3.1 Permitted Concomitant Medications

Rescue Medication (RM) – Dulcolax®

Dulcolax® 5 mg tablets will be dispensed to patients at Visit 1, and re-supplied at the study visits as needed. From Visit 1 and for the duration of the trial, only protocol supplied Dulcolax® is to be used as the “rescue medication” (laxative) - no other laxatives are allowed. As per Dulcolax® package insert (directions for use), Dulcolax® “may be taken 1 to 2 tablets as a single dose per day”.

Patients are instructed to take rescue medication only if it has been at least 72 hours since their last bowel movement. A patient is therefore expected to have no more than two days of RM use in any given week.

Rescue medication usage will be recorded daily via the electronic diary. Sites will review rescue medication use with patients during their study visits and have the option to discontinue participation of patients who do not adhere to rescue medication guidelines.

Patients are advised NOT to take rescue medication for the period from 24 hours before to 72 hours after Day 1 of dosing. This avoids confounding the data collected in the first week of study drug administration and allows for accurate determination of the time to first BM.

Dulcolax® will be distributed to sites by Sharp Corporation. Sites may order additional bulk supplies of rescue medication by submitting a Dulcolax® Request Form. Supplies of Dulcolax® will not be reconciled at the completion of the study. Sites must track inventory of rescue medication supplies for the purpose of ensuring adequate quantities for re-supplying patients as needed. The site’s supply of rescue medication will not be managed nor automatically re-supplied.

3.3.2 Prohibited Prior and Concomitant Medications and Supplements

The following medications, laxatives, and supplements are **prohibited within 15 days** prior to the Screening visit and for the duration of the study, unless otherwise indicated:

- Oral anticholinergic agents (topical and inhaled anticholinergics are allowed)
- Drugs with activity at the 5-HT4, 5-HT3, and 5-HT2b receptors
- Antidiarrheal agents including Pepto Bismol™, kaolin, and opiates
- Drugs known to cause diarrhea such as orlistat, acarbose, misoprostol, and colchicine
- Bile acid sequestrants (cholestyramine and colestipol)
- Amitiza® (lubiprostone)

- Linzess®/Constella® (linaclotide)
- Resolor® (prucalopride)Antibiotics, including rifaximin, and opioids, including tramadol or opiate antidiarrheals (diphenoxylate, and loperamide) are generally prohibited. However, short-term (<15 days) use of opioids or antibiotics for the treatment of AEs or intercurrent illness may be administered during the Screening Period prior to Visit 2 (Day 1) or after randomization in the study as long as they are reported. If a patient needs to be started on an antibiotic or a narcotic during the screening period, the patient's Visit 2 may be delayed to allow for discontinuation of these medications at least 3 days before randomization.

Prohibited drugs when required and used to treat TEAEs are allowed.

The following drugs are allowed only if the patient has been on a **stable dose for the 8 weeks** prior to the Screening/Baseline Period and the patient agrees to remain on this dose for the duration of the study.

- Anticonvulsants
- Antidepressants
- Calcium channel blockers
- Proton pump inhibitors and H₂ antagonists
- Antihistamines that have primarily anti H1 activity (eg, cetirizine, loratadine, and chlorpheniramine)
- Bulking agents (eg, psyllium [Metamucil®] methylcellulose [Citrucel®], calcium polycarbophil)

Thyroid hormone supplementation: levothyroxine (T4) or natural desiccated thyroid hormone or liothyronine (T3) are allowed only if the patient has been on a stable dose for the 30 days prior to the 2-week Screening/Baseline Period and remains on this dose for the duration of participation in the study.

Prohibited Laxatives

All laxatives (except for rescue medication as described in the following list) will be prohibited from the Screening Visit (Visit 1) and onward for the duration of the study (including 2 weeks posttreatment). This includes the following:

- Lactulose
- Stimulant laxatives, including senna (Ex-Lax®) and sennosides (eg, Senokot®), cascara sagrada, anthraquinones, castor oil, aloe, or other
- Osmotic laxatives (eg, polyethylene glycol 3350 [MiraLAX®], magnesium hydroxide [Milk of Magnesia®], magnesium sulfate [Epsom Salts®] sodium biphosphate [Phospho-Soda®], saline laxatives [magnesium citrate], glycerine suppositories, glucitol [Sorbitol®] lactulose)

- Bisacodyl (eg, Dulcolax®, Carter's Little Pills®, Alophen®, Correctol®) and other diphenylmethane laxatives (phenolphthalein). Note: See rescue medication exception in **Section 3.3.1**
- Stool softeners (docusate sodium, eg, Colace®)

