4.1.3 Previous Medications and Diet

At the Screening Visit (Visit 1), the clinical site will ensure the patient is not or has not been on prohibited medications, supplements or investigational agents during the specified time (see **Section 3.3.2**). If the patient has used a prohibited medication within the proscribed time period prior to Visit 1, the site needs to assure that the required washout period for the medication is completed before commencement of the 2-week baseline diary assessments. Previous medications will be documented as described in **Section 3.3**.

The diet history of each patient will be reviewed at Screening (Visit 1) to determine if the patient has been on a stable diet for the last 30 days, and whether the patient agrees to remain on that diet for the duration of the study.

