5.2.2 Visit 2: Randomization / Day 1 of Treatment Period

Study eligibility must be confirmed ***prior to randomization***, including the following:

- Confirm that patient has used only study-supplied rescue medication laxative (Dulcolax[®]) since Visit 1
- Urine drug screen (see **Section 4.3.2** for details)
- Urine pregnancy test, if applicable
- Update medical history and concomitant medications, as necessary

The last 14 days of daily diary entries prior to randomization will be used for determination of baseline data. Only patients who meet the protocol criteria for confirmation of CIC and demonstrate diary and RM compliance are eligible for randomization. This eligibility determination will include:

- A review of the baseline diary entries to ensure patients have completed at least 5 of the 7 days of diary entries in each of the 2 weeks of baseline assessments
- A review of the BM frequency data to ensure < 3 SBMs in each of the 2 weeks of the baseline diary assessment period
- A review of rescue medication use to ensure patients have not used RM for more than 2 days in each baseline week

The eligibility determination based on these criteria will be programmed into the IWRS and the system will report out eligibility (the PI or site staff will not be responsible for evaluating diary data to make the diary-based eligibility determination).

The following procedures will be performed ***only for patients eligible for randomization:***

Procedures ***prior to study drug dosing:***

- Physical examination (including body weight) and vital signs (seated blood pressure, heart rate, respiration, and body temperature)
- 12-lead ECG (semi-recumbent)
- Assess adverse events
- Safety laboratory assessments (hematology, serum chemistry, urinalysis)
- Confirm that patient is on a stable diet and has no significant changes in their consumption of liquids or fiber or their level of activity
- Blood samples for plecanatide/SP-338 concentration and immunogenicity assessments (see **Section 4.3.3** for details)
- Have the patient complete all baseline PRO questionnaires (Per Study Procedure Manual).

The first dose of study drug will be administered at the clinical site under supervision. The time of dosing will be recorded.

The following procedures will be performed ***after study drug dosing:***

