8.4.3 Baseline Definition

For each safety parameter, the most recent valid assessment recorded before randomization will be used as the baseline for all analyses of that safety parameter.

For efficacy parameters, the baseline values will be derived from data collected in the 2-week electronic diary assessment at the end of the Screening Period (baseline). The last 14 days of diary entries prior to Day 1 will be the default standard for derivation of these values.

The baseline SBM (CSBM) weekly rate will be the weekly average number of SBMs (CSBMs) recorded during the 2-week baseline assessment period. Baseline stool consistency, severity of straining during a BM, and abdominal symptoms will be calculated as follows: for each week of the baseline assessment, the weekly average is the sum of the non-missing scores recorded during the week divided by the total number of non-missing scores recorded during that week; the baseline is then equal to one-half of the sum of the two weekly average scores..

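### An opioid started during screening need stop only 3 days before randomization, so up to 11 of the 14 diary days that set SBM eligibility and baseline can be on a constipating drug

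*Combined protocol and SAP*

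**What the plan says.** Section 3.3.2 generally prohibits opioids and antibiotics but permits courses of under 15 days for adverse events or intercurrent illness during screening, provided they are reported. For an antibiotic or narcotic started in screening, its only timing rule is that Visit 2 "may be delayed to allow for discontinuation of these medications at least 3 days before randomization".

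The same fortnight has two uses. Section 5.2.2 states: "The last 14 days of daily diary entries prior to randomization will be used for determination of baseline data". It applies the SBM, diary-completion and rescue checks to those days. Exclusion 19 rejects a patient with three or more "SBM per week for either week of the 2-week baseline diary assessment". Section 8.4.3 takes the efficacy baseline from the same days: "The last 14 days of diary entries prior to Day 1 will be the default standard for derivation of these values".

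For prohibited drugs used before Visit 1, section 4.1.3 is stricter: "the site needs to assure that the required washout period for the medication is completed before commencement of the 2-week baseline diary assessments". Exclusion 3 shows how the protocol regards opioids. It lists patients who currently require "opioid-containing medications or compounds for pain, or has other conditions that require medications known to cause constipation".

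**The concern.** The stricter washout rule covers the more distant exposure, and the weaker one covers exposure that can fall inside the measured window. An opioid taken before Visit 1 must be washed out before the baseline diary starts. An opioid started after Visit 1 may be taken through most of that diary.

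Exclusion 19 does real work here. Under Appendix A, Rome III needs two of six criteria, so a patient can qualify without infrequent stools. The diary count is what keeps out patients whose usual frequency is normal. Opioid days can let such a patient through, and the return to the usual rate after the drug stops then appears as change from baseline, whatever the arm. The patient's baseline, a covariate in the SBM model of section 8.8.1.1, is also too low.

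**Working it through.** **Day count.** The plan gives no figure of its own here. Diary days run from -14 to -1, and randomization is Day 1.

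- Drug-free days required: 3 (days -3 to -1).
- Days that can be on opioid: 14 - 3 = 11 (days -14 to -4), which is 7 of 7 in week 1 and 4 of 7 in week 2.
- If the last dose may fall on day -3, the count is 12.
- A 14-day course, the longest allowed, ending on day -4 starts on day -17, inside the 28-day screening period.

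**Chance of passing exclusion 19.** The documents give no opioid effect and no usual rate for such patients, so these are assumptions: weekly SBM counts are Poisson, the usual rate is 4/week, opioid days halve SBMs, and the opioid days end on day -4. Exclusion 18 is ignored. A pass is at most 2 SBMs in each week.

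| Opioid days | Mean, week 1 | Mean, week 2 | P(pass) |
|---|---|---|---|
| 0 | 4.00 | 4.00 | 0.238 × 0.238 = 0.057 |
| 5 (1 in week 1, 4 in week 2) | 3.71 | 2.86 | 0.283 × 0.456 = 0.129 |
| 11 (7 and 4) | 2.00 | 2.86 | 0.677 × 0.456 = 0.309 |

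**Baseline among those who pass.** The mean baseline is 1.54 with no opioid and 1.29 with 11 opioid days at half rate. With 11 days of complete suppression it is 0.56. Change on return to 4/week is therefore 4 - 1.54 = 2.46, 4 - 1.29 = 2.71 and 4 - 0.56 = 3.44. Most of this is selection on a low count. The opioid itself adds 0.25 to 0.98 SBM/week.

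**Effect on an arm.** Take the worst of these cases (3.44) and let that patient replace one with the mean placebo change assumed in section 8.2 (1.2):

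- Shift in a 30-patient arm mean: (3.44 - 1.2) / 30 = 0.075 SBM/week.
- Standard error of the planned contrast, from the SDs in section 8.2 and without covariate adjustment: sqrt((2.6² + 4.0²) / 30) = 0.87.
- Ratio: 0.075 / 0.87, under 9% of one standard error. Against the planned difference of 3.1 - 1.2 = 1.9 it is about 4%.

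**The case against.** Several provisions put opioid use in front of the site, and the objection that the gap is small is largely right.

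- **Urine opioid screen.** It must be negative before dispensing (Table 2, note d). It covers only methadone, morphine and oxycodone, and it shows status at the visit, not exposure earlier in the diary.
- **Medication update and reporting.** Section 5.2.2 requires an update of concomitant medications before randomization, and section 3.3.2 makes reporting a condition of use. These may reveal the course, but neither says what then happens to the diary.
- **Exclusion 10.** It lets the investigator reject a patient whose medication would "compromise his or her safety or compliance with the study protocol or compromise data collection". That is discretionary.
- **Exclusion 18.** A patient with no SBMs for 11 days is likely to take rescue, and doses on days 1, 4 and 7 of a week would exceed the two-day limit. So pass probabilities that assume complete suppression and ignore this check should not be relied on. At half suppression the check need not trigger: section 3.3.1 expects no more than two rescue days a week from a patient who follows the 72-hour rule.
- **Room in the analysis.** Section 8.4.3 calls the 14-day window a default but defines no alternative. The per-protocol analysis removes major deviations, but a course that section 3.3.2 permits is not clearly a deviation.

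A reader might also see a contradiction in exclusion 15 ("The patient has taken a protocol-prohibited medication prior to randomization"), which read literally bars the patient whom section 3.3.2 admits. The specific permission in 3.3.2 ordinarily governs, so this is a matter of wording. Nor does the point extend to antibiotics: the 3-day rule covers them, but the documents state no effect of antibiotics on bowel frequency.

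What stands is that none of these provisions requires the baseline diary to be moved.

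**Conclusion.** The gap is real and minor. The day count rests on the text alone. The pass probabilities (6%, 13% and 31%) rest on the stated assumptions and show direction and rough size only.

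A reader might infer a biased treatment effect or a loss of power. The documents support neither. The exposure occurs before randomization, so affected patients fall into any arm with equal probability. The documents give no frequency of opioid use in screening, so no power loss can be calculated. On the worst case above, one affected patient shifts an arm mean by at most about 0.08 SBM/week against a standard error of about 0.87. The responder definition in section 2.4.1.1 does not use baseline at all.

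The harm is confined to an occasional wrong eligibility decision and too low a baseline in the patients concerned, who are probably few.

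**What to change.** In section 3.3.2, state that if an opioid is started during screening, Visit 2 and the 14-day baseline diary will be moved so that the opioid is stopped at least 3 days before the first baseline diary day. That means at least 3 + 14 = 17 drug-free days before Day 1, and no baseline day on opioid.

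Use the recorded stop date to set the baseline window prospectively, for example by having the site enter it in the IWRS. This cannot be left to the analysis, because section 4.2.1 says that diary data entered before the baseline window are not kept.

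The cost is up to about 14 more days of screening (17 - 3) for the few patients affected, plus a short text change and one date field. Section 3.3.2 already allows Visit 2 to be delayed, and section 1 gives the 28-day interval only as an ideal. Sample size and other patients are unaffected. Rewording exclusion 15 to refer to section 3.3.2 is optional tidying.
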